5.2.1.5. Concomitant treatments

The anatomical therapeutic chemical classification (ATC code = 5 digits) is composed of 4 levels:

- The first (1 digit) represents the anatomo-physiological class.
- The second (2 digits) represents the pharmacological class.
- The third (1 digit) represents the pharmacological sub-class.
- The last (1 digit) represents the therapeutic class.

The existence of a concomitant treatment (Yes, No) is defined from the presence, or not, of an Anatomical therapeutic chemical classification and/or Preferred name.

The periods considered for the analysis are:

At inclusion for which treatments:

- With start date \leq inclusion date and stop date \geq inclusion date or missing are taken into account. Inclusion date is equal to the date of inclusion visit, *i.e.* A000/D000 visit date.

Before the treatment period for which treatments:

- With start date $<$ first IMP intake date are taken into account.

During the treatment period for which treatments:

- With start date \geq first IMP intake date and $<$ (*), or
- With start date \leq first IMP intake date and stop date \geq first IMP intake date or missing

After the treatment period for which treatments:

- With start date \geq (*), or
- With start date \leq (*) and stop date $>$ (*) or missing.

(*)*max (first intake date of last cycle + 28 days of trifluridine/tipiracil, first intake date of last cycle + 28 days of futuximab/modotuximab)*

The following rules for substitution of missing or incomplete start and stop dates are so that the concomitance period is maximised:

CL3-95026-001 - Statistical Analysis Plan | VV-TMF-130355 | 1.0

Table (5.2.1.5) 1 - Substitution rules of concomitant treatments intake dates

Date to substitute		Substituted date
Start date	../mmm/yyyy	If the year and the month are the same as the year and the month of inclusion then Start date = Inclusion date , otherwise Start date = 01/mm/yyyy
/yyyy	If the year is the same as the year of inclusion then Start date = Inclusion date , otherwise Start date = 01/01/yyyy
/....	If stop date is non-missing and inferior to inclusion date then: Stop date Else: Inclusion date
Stop date	../mmm/yyyy	If patient died same month and year then Date of death Else Last day of the month/mmm/yyyy
/yyyy	If patient died same year then Date of death Else 31/DEC/yyyy
/....	If patient died then Date of death Else No substitution (i.e., treatment considered as still ongoing)

Note:/mm/yyyy = missing day
..../..../yyyy = missing day and month
..../.... = missing date

CL3-95026-001 - Statistical Analysis Plan | VV-TMF-130355 | 1.0

The following rules for substitution of totally or partially missing start and stop dates are used for concomitant treatments (only further anti-tumour therapy):

Table (5.2.1.5) 2 - Substitution rules of further anti-tumour therapy intake dates

Date to substitute		Substituted date
Start date	.../mmm/yyyy	If the year and the month are the same as the year and the month of the last Last IMP intake date otherwise 01/mm/yyyy
	.../.../yyyy	If the year is the same as the year of the last IMP intake date then Last IMP intake date , otherwise 01/01/yyyy
	.../.../....	Last IMP intake date
Stop date	.../mmm/yyyy	If patient died same month and year then Date of death Else Last day of the month/mmm/yyyy
	.../.../yyyy	If patient died same year then Date of death Else 31/DEC/YYYY
	.../.../....	If patient died then Date of death Else No substitution (i.e., treatment considered as still ongoing)

Note: .../mm/yyyy = missing day

.../.../yyyy = missing day and month

.../.../.... = completely missing date

The last IMP intake corresponds to the real last IMP intake within the analysis period.

6. APPENDIX B: EFFICACY

6.1. Non-confirmed Best overall response

Best overall response is defined as the best overall response across all time points excluding “Follow-up” e-CRF information. If applicable, responses recorded after intercurrent events will be excluded.

When SD is believed to be best overall response, it needs to be assessed a minimum of 6 weeks after study inclusion. Otherwise, the best overall response will be NE, unless any PD was further documented, in which case BOR will be PD.

A patient dead because of progression* before the first assessment planned per protocol (8 weeks) will be considered as ‘early death’. If a patient progressed* before this first assessment, he will be considered as ‘early progressive’. If any of these two events occur, the overall response of the patient will be resumed as progression (PD).

*: Progression/Death due to progression before the end of cycle 2:
According to tumoral evaluation.
Withdrawal reason status.

In case of best overall response missing under the studied period, this one will be considered as Non-Evaluable (NE).

Complete response (CR) and partial response (PR) will not be confirmed following initial documentation of overall response.

Table (6.1) 1 - BOR when confirmation of CR and PR not required

Overall response	Overall response	BOR
First time point (i)	Next time point (i+1)	
CR	Whatever the overall response	CR
PR	Whatever the overall response other than CR	PR
SD	PD	SD (if the time length between the study inclusion and the SD is \geq 6 weeks), otherwise, PD
SD	SD or NE or missing	SD (if the time length between the study inclusion and one of the SD is \geq 6 weeks), otherwise, NE unless any PD was further documented
PD	Whatever the overall response	PD
NE or missing	PD	PD
NE or missing	NE or missing	NE

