7.2.4.4. Target and Non-target Response Assessments

Tumour assessments will be performed as per RECIST version 1.1³¹ at baseline and then every 8 weeks from C1D1 (\pm 7 calendar days) until radiologic progression, death or end of study, whichever occurs first. The definition of responses for Target and Non-target lesions is presented in Table (7.2.4.4) 1 and Table (7.2.4.4) 2 respectively.

Table (7.2.4.4) 1 - Target lesions response definitions

TARGET LESIONS	
Lesions Response	Definition
Complete Response (CR)	The disappearance of all target lesions. Any pathological lymph nodes must have reduction in short axis to < 10 mm.
Partial Response (PR)	At least a 30% decrease in the sum of diameters of the target lesions, taking as a reference the baseline sum diameters.

TARGET LESIONS	
Progressive Disease (PD)	At least a 20% increase in the sum of diameters of the target lesions, taking as a reference the smallest sum on study, including the baseline sum. In addition to the relative increase of 20%, the sum must also demonstrate an absolute increase of at least 5 mm. Definitive new lesion presence also indicates progression.
Stable Disease (SD)	Neither sufficient shrinkage to qualify for PR nor sufficient increase to qualify for PD, taking as a reference the smallest sum diameter while on study.

Table (7.2.4.4) 2 - Non-target lesions response definitions

NON-TARGET LESIONS	
Lesions Response	Definition
Complete Response (CR)	The disappearance of all non-target lesions and normalisation of tumour marker level. All lymph nodes must be non-pathological morphologically (i.e. , < 10 mm in short axis in size).
Non-CR/Non-PD	A persistence of ≥ 1 non-target lesion(s) and/or maintenance of tumour marker level above the normal limits (not reaching the extent of ‘unequivocal progression’).
Progressive Disease (PD)	Unequivocal progression of existing non-target lesions (see definition below). (Note: the appearance of one or more new lesions is also considered progression).

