PR	PD	SD provided minimum criteria for SD duration met, otherwise, PD
PR	NE	SD provided minimum criteria for SD duration met, otherwise NE
NE	NE	NE

CR = complete response, PR = partial response, SD = stable disease, PD = progressive disease, and NE = Not evaluable.

¹ = If a CR is truly met at first time point, then any disease seen at a subsequent time point, even disease meeting PR criteria relative to baseline, makes the disease PD at that point (since disease must have reappeared after CR). Best response would depend on whether minimum duration for SD was met. However, sometimes 'CR' may be claimed when subsequent scans suggest small lesions were likely still present and in fact the patient had PR, not CR at the first time point. Under these circumstances, the original CR should be changed to PR and the best response is PR.

Special notes on response assessment

When nodal disease is included in the sum of target lesions and the nodes decrease to 'normal' size (< 10 mm), they may still have a measurement reported on scans. This measurement should be recorded even though the nodes are normal in order not to overstate progression should it be based on increase in size of the nodes. As noted earlier, this means that patients with CR may not have a total sum of 'zero' on the case report form (e-CRF).

In trials where confirmation of response is required, repeated 'NE' time point assessments may complicate best response determination. The analysis plan for the trial must address how missing data/assessments will be addressed in determination of response and progression. For example, in most trials it is reasonable to consider a patient with time point responses of PR-NE-PR as a confirmed response.

Participants with a global deterioration of health status requiring discontinuation of treatment without objective evidence of disease progression at that time should be reported as 'symptomatic deterioration'. Every effort should be made to document objective progression even after discontinuation of treatment. Symptomatic deterioration is not a descriptor of an OR: it is a reason for stopping study therapy. The OR status of such patients is to be determined by evaluation of target and non-target disease as shown in [Tables 1–3](#).

Conditions that define 'early progression, early death and inevaluability' are study specific and should be clearly described in each protocol (depending on treatment duration, treatment periodicity).

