5.2. Specific analytic definitions and data handling conventions

5.2.1. Study patients: Disposition, baseline characteristics and follow-up

5.2.1.1. Disposition of patients

All treatment withdrawal reasons occurred in the study will be taken into account (adverse event, protocol deviation, progressive disease (radiological progressive disease, clinical progressive disease, radiological and clinical progressive disease), non-medical reason (consent withdrawal from study treatment, consent withdrawal including survival follow-up), lost to follow-up, physician decision or other medical reason).

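### SAP 6.1 can score clinical progression without imaging as a best overall response of PD, and does not say whether that rule or Table (6.1) 1 prevails

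*SAP*

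**What the plan says.** SAP 3.4 summarises BOR by RECIST 1.1 using the investigator's tumour assessment. SAP 1.1 keeps it as the only secondary endpoint still assessed.

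SAP 6.1 adds a rule for early events. Death from progression "before the first assessment planned per protocol (8 weeks") is an early death. For progression it says "If a patient progressed* before this first assessment, he will be considered as" early progressive. The consequence of either is stated without exception: "If any of these two events occur, the overall response of the patient will be resumed as progression (PD"). The asterisk leads to a footnote with a different limit, "Progression/Death due to progression before the end of cycle 2", and two sources on separate lines: the tumour evaluation and "Withdrawal reason status". Nothing joins the two lines.

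SAP 5.2.1.1 lists the progression-type withdrawal reasons as "progressive disease (radiological progressive disease, clinical progressive disease, radiological and clinical progressive disease"). Protocol 5.8.1 describes clinical progressive disease as symptomatic deterioration.

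Protocol Appendix 7 states: "Symptomatic deterioration is not a descriptor of an OR: it is a reason for stopping study therapy". It scores such patients on their target and non-target lesions. Protocol 7.2.1 stops treatment for clinical progression without radiological support but continues scans until radiological progression.

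Table (6.1) 1 keeps a first PR unless a CR follows. It keeps an SD assessed at least 6 weeks after inclusion, whether PD, SD, NE or nothing follows.

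**The concern.** There are two faults. First, the withdrawal reason stands beside tumour evaluation as evidence of progression, with no restriction to radiological progression. A clinical judgement can then appear as PD in a table described as RECIST 1.1.

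Second, the body text, the footnote and the table are three rules for the same participant with no order among them. They can disagree, and the programmer would have to choose. At stake is the split between PR, SD, PD and NE in the only efficacy endpoint the SAP retains.

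**Working it through.** **Inputs.** Cycle length is 28 days (Protocol 6.1.1.3). The first scan is due 8 weeks from C1D1, ±7 days (Protocol 7.2.4.4). The first dose is within 3 days of inclusion (Protocol 4.1.1). The minimum for SD is 6 weeks, or 42 days, from inclusion (SAP 6.1). A last cycle appears to end 27 days after its first intake (SAP 5.1.2, where the text is partly garbled). C1D1 is taken as Day 1.

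**The two limits on schedule.** 2 × 28 = 56 days = 8 weeks, so body text and footnote agree nominally.

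**Where scans fall.** 8 weeks from Day 1 is Day 57, so the permitted window is Day 50 to Day 64, which is 15 days.

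- Cycle 2 on time: Day 29 + 27 = Day 56. Days 50 to 56 are on or before the cut-off: 7 of 15 days, 6 of them strictly before.
- Cycle 2 starting 8 days late: it ends on Day 64, and all 15 days are on or before the cut-off. From a 9-day delay all 15 are strictly before.
- Latest start counting 30 days from a Day 12 trifluridine/tipiracil dose (Protocol 8.11.1): Day 42, so cycle 2 ends on Day 42 + 27 = Day 69.

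**Three participants, each withdrawn for clinical progression only, with the footnote lines read as alternatives.**

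| Case | Early rule | Table (6.1) 1 |
|---|---|---|
| A. Withdrawn Day 35, never scanned | PD | NE |
| B. Withdrawn Day 35, withdrawal-visit scan Day 50 shows SD | PD | SD |
| C. First scan Day 52 shows SD, withdrawn Day 55 | PD if the footnote cut-off or the nominal 8-week date governs; not triggered if the scan actually done governs | SD |

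With PR in place of SD, B and C are PR by the table.

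**Check of case B.** The withdrawal visit is within 4 weeks of stopping, so up to Day 35 + 28 = Day 63. A scan is due there if none was done in the previous 8 weeks. With a baseline scan 14 days before C1D1, Day 50 is 49 + 14 = 63 days later, which exceeds 56. Day 50 is 49 to 52 days after inclusion, above 42. SAP 5.1.2 accepts tumour assessments up to 30 days after the last intake; with a last dose on Day 29 the gap is 21 days. The withdrawal visit is not a Follow-up page, which is what SAP 6.1 excludes. This case needs neither an early scan nor a cycle delay, and the rule is met on either reading of the first assessment.

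Case B has one proviso. SAP 6.1 also drops responses after intercurrent events, if applicable. The SAP defines none for this part; the protocol's list, written for the Randomised part, includes treatment discontinuation. If that were applied, the Day 50 scan would be dropped and the table would give NE. The rule would still give PD.

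**Check of case C.** Day 52 is 51 to 54 days after inclusion, above 42. Symptomatic deterioration is not an overall response, so the applicable row is SD followed by NE or missing, which gives SD.

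**Weight of one participant.** 100/25 = 4.0 percentage points at the planned size, 100/12 = 8.3 and 100/6 = 16.7 for smaller numbers.

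**The case against.** The strongest reply is that the SAP does not tell anyone to discard an earlier SD or PR. The body text confines early progression to the time before the first assessment, the asterisk only explains how progression is identified, BOR is defined as the best response across time points, and the table preserves PR. On schedule the two limits coincide, so case C needs an early scan and then withdrawal within about six days. This stands: a reader might infer that the SAP prescribes overwriting a response already seen, and the documents do not support that. They permit it, because precedence is missing. Case B does not depend on the narrow timing.

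Next, Appendix 7 says conditions defining early progression, early death and inevaluability are study specific. An early rule is therefore allowed in principle. But the appendix expects it in the protocol, and Protocol 7.2.5 contains none.

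Third, the two footnote lines might both be required. Then withdrawal reason alone would not give PD. The second line would add little on that reading, so treating them as alternatives is more natural, but the SAP does not settle it.

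Last, the consequences are small. The summary is descriptive and single-arm, so the open-label setting cannot bias a comparison. The error runs towards PD, against the treatment. Moving a participant between PD and NE leaves the response and disease-control shares unchanged if everyone stays in the denominator. The waterfall plot in SAP 3.4 and the disposition categories give independent views. All of this stands and limits the weight of the point.

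**Conclusion.** The point holds as a conflict that should be resolved. On the natural reading of the footnote, clinical progression without imaging becomes PD in a BOR labelled RECIST 1.1, contrary to Appendix 7 and SAP 3.4. Separately, the early rule and Table (6.1) 1 can give different results for the same participant, with no stated precedence.

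The size is about 4 percentage points per reclassified participant at the planned 25. The actual number treated is not given, and the part was discontinued, so the weight could be larger. How many participants are affected is unknown. A reader might try to estimate this from the median PFS values of 2.1 and 4 months in Protocol 10.1.2.8. Those are assumptions for an interim comparison in the cancelled Randomised part, and they would count every early progression or death, including those where the rules agree. They do not measure misclassification.

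The conclusion assumes that C1D1 is Day 1, that the footnote lines are alternatives, and, for case B giving SD, that treatment discontinuation does not exclude the withdrawal-visit scan.

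**What to change.** Amend SAP 6.1 as follows:

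- State that Table (6.1) 1 governs whenever an evaluable post-baseline tumour assessment exists. Radiological progression on any scan, early or not, is then handled by the table.
- Restrict the early rule to participants with no evaluable post-baseline assessment, and assign PD there only for death due to progression. Name the e-CRF field that identifies such a death.
- Report withdrawal for clinical progression without imaging as NE, on its own line labelled *clinical progression, not imaged*.
- Use one time limit in body text and footnote. A day count from C1D1 would be workable, since a participant who stops in cycle 1 has no cycle 2 to end.
- Say whether treatment discontinuation counts as an intercurrent event for BOR in this part.

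The cost is a few sentences and one derivation, with no new data. The downside is that some participants may move from PD to NE or SD. If the tables already exist, a footnote stating the rule used and a listing of participants whose PD rests on withdrawal reason would give readers the same information.

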7. APPENDIX C: SAFETY

The **periods** considered **for the analysis** of adverse events, deaths and clinical laboratory evaluation are:

- During the treatment period:
 - With date \geq first IMP intake date and \leq last IMP intake date as defined in the [Section 5.1.5](#) + 30 days.
- After the treatment period:
 - With date $>$ last IMP intake date as defined in the [Section 5.1.5](#) + 30 days.

7.1. Adverse events

Each **medical concept of adverse events coded according to the internal "multiple medical concept" process** is taken into account as a single adverse event in the statistical analysis.

The modalities of the adverse event (onset and end dates, severity, seriousness, action taken, additional therapy, relationship, outcome...) replicated by default to each medical concept are also taken into account in the statistical analyses.

Emergent adverse events on treatment are defined as all adverse events:

- Which occur between the first IMP intake date (included) and the last IMP intake date "+ 30 days" (included), considering the definition of last study drug intake defined in [Section 5.1.5](#)

or

- Which occur before the first IMP intake date and which worsen (in terms of severity) or become serious according to the investigator opinion between the first IMP intake date (included) and the last IMP intake date "+ 30 days" (included), considering the definition of last study drug intake defined in [Section 5.1.5](#).

Note: Adverse events occurring or worsening or becoming serious on the day of the first study drug/associated agent intake (if any) is considered as emergent.

Serious adverse events are defined from investigator assessment as all adverse events fulfilling at least one of the following seriousness criteria for immediate notification: death, hospitalisation or prolongation of hospitalisation, medically important, life-threatening, disability/incapacity or congenital anomaly.

A fatal adverse event corresponds to an adverse event with "Fatal" as outcome.

Adverse events related to Trifluridine/tipiracil correspond to adverse events associated with the answer "Related" to the "Is this event related to Trifluridine/tipiracil" question.

Adverse events related to Futuximab/modotuximab correspond to adverse events associated with the answer "Related" to the "Is this event related to Futuximab/modotuximab" question.

Adverse events related to the combination correspond to adverse events associated with the answer "Related" to the "Is this event related to Trifluridine/tipiracil" question and/or with the answer "Related" to the "Is this event related to Futuximab/modotuximab" question.

Adverse events related to disease progression correspond to adverse events associated with the answer "Related" to the "Is this event related to disease progression" question.

The following information will be taken into account:

- For the analyses where the severity of the adverse event is considered, the worst severity from the day of emergence and during the studied period (*i.e.* between the first study drug/associated agent intake date (included) and the last study drug/associated agent intake date (as defined in [Section 5.1.5](#)) “+ 30 days” (included) will be taken into account.
- The number of patients by worst grade: for each patient, system organ class and preferred term, we analyze the worst grade of events.
- The number of events by worst grade: for each patient, system organ class and preferred term, we analyse the worst grade of each event. The percentage will be calculated as the number of events of the PT concerned at grade X divided by the total number of events of the PT concerned.
- For the analyses where the action taken regarding the study drug and the additional therapy requirement are considered, all the actions taken and additional therapy requirements recorded from the day of emergence and on the studied period will be taken into account.
- However, in case of an episode of an emergent adverse event leading to studied treatment withdrawal reported after the last study drug/associated agent intake date (as defined in [Section 5.1.5](#)) “+ 30 days”, the adverse event will be considered as leading to studied treatment withdrawal during the studied period.
- Seriousness is judged by event: if one episode is serious (whatever the time it occurs), the whole event will be considered as serious.
- A severe adverse event corresponds to an adverse event with NCI CTCAE grade 3, 4 or 5.
- Any grade corresponds to an adverse event with NCI CTCAE grade 1, 2, 3, 4 or 5.
- All multicoded events will be taken into account in the analyses.
- For the analysis of recovered emergent adverse event during / after treatment period, a TEAE is considered as recovered “during treatment period” (“after end of treatment period”, respectively) if the associated outcome is “recovered” or “recovered with sequelae” and occurs between the first study drug/associated agent intake date and the last study drug/associated agent intake date (as defined in [Section 5.1.5](#)) “+ 30 days” (included) (strictly after the last study drug/associated agent intake date (as defined in [Section 5.1.5](#)) “+ 30 days”, respectively).

The following rules are applied in case of missing severity:

Table (7.1) 1 - Treatment-emergence of adverse events in case of missing severity/grade (if any)

Severity/Grade		Adverse event considered as	
Nearest before the first study drug/associated agent intake date	During the study period		
Missing	Missing	→	Treatment-emergent
Missing	Grade 1	→	Non treatment-emergent
Missing	Grade 2, 3, 4 or 5	→	Treatment-emergent
Grade 1, 2, 3	Missing	→	Treatment-emergent
Grade 4	Missing	→	Non treatment-emergent

CL3-95026-001 - Statistical Analysis Plan | VV-TMF-130355 | 1.0

The rules for substitution of missing or incomplete episode date (onset date, dates of the six seriousness criteria and dates of change of severity and action taken) are as follows:

Table (7.1) 2 - Substitution rules of AE dates

Date to substitute	Substituted date (Episode date)
../mmm/yyyy	If same month and year than first study drug/associated agent intake date then: First study drug/associated agent intake date Else: 01/mmm/yyyy
•/yyyy	If same year than first study drug/associated agent intake date then: First study drug/associated agent intake date Else: 01/JAN/yyyy
•/....	First study drug/associated agent intake date

Note: ..mm/yyyy = missing day
..../yyyy = missing day and month
..../.... = missing date

The rules for substitution of missing or incomplete recovery dates, in case of AE outcome "recovered" or "recovered with sequelae" are as follows:

Table (7.1) 3 - Substitution rules of recovery date

Date to substitute	Substituted date
../mmm/yyyy	If same month and year than date of AE last information ^(*) then: Date of AE last information Else: Last day of the month /mmm/yyyy
..../yyyy	If same year than date of AE last information ^(*) then: Date of AE last information Else: 31/DEC/yyyy
..../....	Date of AE last information^(*)

Notes:
- ..mm/yyyy = missing day,
..../yyyy = missing day and month,
..../.... = missing date.

^(*) Date of AE last information is defined as the maximum between onset date, dates of change of severity and action taken and dates of the six seriousness criteria for this adverse event.

